Randomization will be done through an independent study coordinator or research fellow other than the one who is assessing the outcomes. Patients will be randomly assigned to one of the two groups as 1:1 ratio.

The nurse who is responsible for operating the radiofrequency generator will be the only one informed about the randomization results through the unblinded study coordinator. The physician and the patient will both be blinded.

Intravenous access will be inserted for all patients and mild sedation with midazolam will be given according to the patient needs.

With the C-arm guidance a 20-gauge radiofrequency needles with 10mm active tips will be used to ablate 3-4 lumbar facet medial branches.

At each level, needles will be adjusted to optimize sensory and motor stimulation. For each nerve lesion, correct placement is confirmed using electrostimulation at 50Hz, with concordant sensation achieved at 0.5V or less. Before denervation, multifidus stimulation and the absence of leg muscles contractions is verified with electrostimulation at 2Hz.

The radiofrequency lesions will then be carried out at 80°C (group 1) or

90°C (group 2) for 90 seconds twice to produce the desired lesions of the medial branches.

• Data Collection:

Study data for follow-up visits will be collected by one of 3 ways. The follow-up visit questionnaires can be filled in-person, sent out to patients by mail or completed over the phone, whichever is more convenient for the patient.

Collected data will then be inputted and managed using REDCap (Research Electronic Data Capture) tools hosted at Cleveland Clinic. REDCap is a secure, web-based application designed to support data capture for research studies, providing:

1) An intuitive interface for validated data entry.

2) Audit trails for tracking data manipulation and export procedures.

3) Automated export procedures for seamless data downloads to common statistical packages.

4) Procedures for importing data from external sources.

• Patient Demographics:

- Age
- Sex
- Smoking
- BMI
- History of back surgeries.

Page ${\bf 9}$ of ${\bf 16}$

Protocol Version 3 Revision Date: 10/15/2019

- Diabetes mellitus.
- Response to diagnostic blocks

• Patient Baseline data:

- Preoperative and baseline pain score will be collected using Visual Analog Scale (VAS)
- Pain Questionnaires:
 - Pain Disability Index (PDI).
 - McGill Pain Questionnaire.
 - Beck Inventory (BI)
- Oral pain medications in morphine sulfate equivalent mg/day.

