• Technique related data:

- The temperature of the probe used (80°C or 90°C)
- Duration of application of the RF probe is 90 seconds twice using 10mm active tip probe.
- Sensory stimulation 0.5mAmp
- Needle size 20G
- The number of ablated nerves.
- Side/Laterality.

• Outcomes Data:

Outcomes will be measured at baseline and 1, 3, 6 and 12 months follow-up visits post-procedure.

Primary outcomes:

Overall pain relief (i.e. percent of improvement) at each visit mentioned above.

Secondary outcomes:

- Postoperative Pain Scores in the subsequent visits using VAS at each visit mentioned above.
- Pain Questionnaires:
 - Pain Disability Index (PDI).
 - McGill Pain Questionnaire.
 - Beck Inventory (BI)
- Number of repeats of procedure in the first year after index procedure.

• Consumption of oral opioids in mg oral morphine equivalents recorded at the baseline before the procedure and then in the follow-ups post-procedure (1, 3, 6 and 12months).

- This table summarizes the morphine equivalent doses for the most commonly used morphine derivatives (7).

Drug Name	Oral dose equivalent to 30mg oral morphine sulfate	IV dose equivalent to 30mg oral morphine sulfate			
Morphine sulfate	30 mg (1:1 ratio)	10 mg (1:3)			
Hydromorphone	7.5 mg (1:4 ratio)	1.5 mg (1:20)			
Meperidine	300 mg(10:1 ratio)	100 mg (3.33:1)			
Methadone	12mg(1:2.5 ratio)	10 mg (1:3)			
Oxycodone	15 mg(1:2 ratio)	N/A			
Hydrocodone	30 mg(1:1 ratio)	N/A			
Codeine	200 mg(6.66:1 ratio)	120 mg (4:1)			

- The following formula will be used for Fentanyl transdermal patch:

- \circ 25 µg/h is equivalent to 87.5 mg morphine/24h
- \circ 50 µg/h is equivalent to 175 mg morphine/24h
- \circ 75 µg/h is equivalent to 262.5 mg morphine/24h
- \circ 100 µg/h is equivalent to 350 mg morphine/24h

• Adverse Events:

- Persistent paresthesia (yes/no)
- Nerve injury (yes/no)
- Infection (yes/no)
- Bleeding (yes/no)

• Data Analysis:

Standard descriptive statistics will be used to compare the randomized groups on baseline variables. Any obviously imbalanced co-variables (say, with a standardized difference greater than 0.20 in absolute value) will be adjusted for in both primary and secondary analyses. Our primary analysis will be intent-to-treat.

Primary Hypothesis:

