Graphically displayed over follow-up times (1, 3, 6 and 12 months) using boxplots containing the median, quartiles and outliers. At each follow-up time point (1,3, 6 and 12 months) we will assess whether 80°C and 90°C RFA temperatures differ with respect to the percentage of pain relief using the Wilcoxon rank-sum test. The significance criterion will be 0.05/4=0.0125 at each time, using a Bonferroni correction to control the type I error at 0.05 for the primary hypothesis. In addition to the P-value, the estimated median percentage of pain relief for each group and difference in medians with confidence intervals will be reported. The estimated probability of pain relief at 90°C being better than at 80°C with confidence interval will be reported, since the Wilcoxon rank sum test has a null hypothesis that this probability is 0.50. All the confidence intervals will be estimated based on bootstrapped standard error with 10,000 bootstrap replications (8).

Interim analyses:

Interim analyses will be conducted for efficacy and futility at each 25% of the maximum enrollment (see Sample Size Considerations) using a group sequential design and gamma spending function (using gamma = -4 for efficacy and -2 for futility). P-value boundaries for efficacy (futility in parentheses) will be P \leq 0.0016 (P>0.957), P \leq 0.0048 (P>0.719), P \leq 0.0147 (P>0.239), and P \leq 0.0440 (P>0.0040) at looks 1 through 4, respectively.

• Secondary hypotheses: We will compare randomized groups on the following variables:

VAS pain scores/Pain Disability Index (PDI)/McGill Pain questionnaire scores/Beck Inventory (BI) scores.

While the detailed description below focuses on the VAS pain score outcome for brevity, the analysis approach will be the same for Pain Disability Index (PDI), McGill Pain questionnaire scores, and Beck Inventory (BI) scores.

Graphical analysis will be undertaken to describe the degree of pain reduction observed in patients undergoing each treatment. The association between RFA temperature and pain reduction will be performed using a mixed effects model adjusting for time interval and also for baseline pain score to increase precision. We will assess the group-time interaction and assess treatment effects at each time if interaction P <0.15. The mixed model will account for potential intra-subject correlation of repeated VAS pain measurements within a patient using a spatial

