correlation structure. A model-based Wald test for regression model coefficients will be used to evaluate whether or not RFA temperature affects mean pain reduction.

Opioid Consumption:

As preliminary retrospective study showed, postoperative opioid consumption is largely binary in nature for this patient's population, as over 60% of our patients did not take any opioids. Thus, postoperative opioid consumption within a year of the first RFA will be analyzed as a binary outcome, i.e., any versus none (however, dosage information among the subset of patients taking any opioids will be described using medians and quartiles for each group). Multivariable logistic regression will be used to estimate the adjusted relative risk for postoperative opioid use comparing patients undergoing RFA at 90°C to patients undergoing RFA at 80°C. A logistic model-based Wald test for regression coefficients will be used to test the hypothesis of the effect of temperature on the postoperative opioids use (i.e., whether or not the relative risk is different from a value of 1.0).

Number of repeat of RFA procedures

Need for repeated RFA procedure over one year period will be analyzed as a count variable using a proportional odds logistic regression model. If the number of repeats greater than 1 is very rare, we will use a binary outcome of any RFA procedure comparing two groups of patients.

Complications:

Incidence of each individual complication will be reported for each group, with confidence intervals. Possible adverse events (persistent paresthesia, nerve injury, bleeding and infection) will be summarized into a single composite binary outcome, i.e., any versus none. The risk of experiencing one or more adverse events will be compared between RFA at 90°C and RFA at 80°C groups using logistic regression.

Type I error will be controlled at 5% for the secondary outcomes using the Bonferroni correction for simultaneous hypotheses. SAS 9.3 software (SAS Institute, Cary, NC) and R statistical software version 2.7.2 (The R Foundation for Statistical Computing, Vienna, Austria) will be used for all analyses and graphics.

Sample size considerations:

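### The opioid model names no covariates; always including baseline opioid use, which is already collected, would gain precision at almost no cost

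*Combined protocol and SAP*

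**What the plan says.** All references are to the combined protocol and SAP.

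- **Data Analysis, Opioid Consumption.** Use within a year of the first procedure is analysed as any versus none: "Multivariable logistic regression will be used to estimate the adjusted relative risk for postoperative opioid use". Temperature is tested by a Wald test on the logistic coefficient. No covariate is listed, and the step from a logistic model to a relative risk is not described.
- **Patient Baseline data** lists "Oral pain medications in morphine sulfate equivalent mg/day", and **Secondary outcomes** repeats it: "Consumption of oral opioids in mg oral morphine equivalents recorded at the baseline before the procedure".
- **Data Analysis, opening paragraph.** The general rule, for primary and secondary analyses alike: "Any obviously imbalanced co-variables (say, with a standardized difference greater than 0.20 in absolute value) will be adjusted for".
- **Secondary hypotheses.** The VAS model is fitted "adjusting for time interval and also for baseline pain score to increase precision", and "the analysis approach will be the same for Pain Disability Index (PDI), McGill Pain questionnaire scores, and Beck Inventory (BI) scores". Opioid use is not in that list.

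**The concern.** The plan gives its own reason for putting the baseline value into the models for the four scale scores: precision. The same reason applies to opioid use, which is also measured before and after the procedure, yet the opioid paragraph does not say so. Read literally, baseline use enters only if the arms happen to differ on it. Two analysts could fit different models and both claim to have followed the plan.

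At stake is the precision of one Bonferroni-corrected secondary outcome. Validity is not at stake: under randomisation the comparison without baseline use is unbiased and its Wald test is valid.

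**Working it through.** **1. The plan's own figures.** No effect, power or sample size is stated for opioid use, so there is no opioid figure to reproduce. The arm size comes from Sample size considerations. The primary calculation there does reproduce. The tabulated distributions give P(90°C better) = 0.648 and a tie factor of 0.979. With two-sided 0.0125 and 90% power, N = (z_α + z_β)² × tie factor / [3(p − 0.5)²] = 213.8, or 218.4 without the tie factor, against the stated 216. The maximum with interim looks is 237, or about 118 per arm.

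**2. How often the imbalance rule admits baseline use.** With no true difference, the standardised difference has standard deviation of about √(2/118) = 0.130. So P(|d| > 0.20) = 2[1 − Φ(0.20/0.130)] ≈ 0.124. Simulating a binary covariate gives 0.127 at 40% prevalence and 0.129 at 30%. The plan offers 0.20 only as an example: a cut-off of 0.15 gives 25–26%, and 0.25 gives about 6%. If the trial stops early the rate rises, to about 18% at 178 patients (0.75 × 237) and 28% at 119 (0.50 × 237).

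**3. Gain from always adjusting.** Inputs assumed, because the documents do not give them:

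- 40% baseline users. The only related figure concerns postoperative use in the retrospective study, "as over 60% of our patients did not take any opioids".
- A conditional odds ratio of 0.50 for 90°C against 80°C, and 118 per arm.
- Five pairs of later-use rates at 80°C, for baseline users and non-users.

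The marginal risk is 0.4 × (risk in users) + 0.6 × (risk in non-users). For the 50/30 row at 80°C: 0.4 × 0.50 + 0.6 × 0.30 = 0.380. Halving the odds gives 0.333 and 0.176 at 90°C, so the marginal risk is 0.239 and RR = 0.239/0.380 = 0.63. Simulated trials compared the plan's rule (adjust only if |d| > 0.20) with always adjusting and standardising:

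| Later use at 80°C, users / non-users | Marginal RR | Fall in variance of log RR, against the rule | Power at two-sided 0.05, rule → always |
|---|---|---|---|
| 90% / 5% | 0.88 | about 53% | 10% → 25% |
| 70% / 15% | 0.71 | about 16% | 42% → 54% |
| 60% / 20% | 0.66 | about 8% | 54% → 60% |
| 50% / 30% | 0.63 | about 2% | 65% → 66% |
| 36% / 36% | 0.61 | 0% | 67% → 67% |

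The rows share a conditional odds ratio, not a marginal effect, so power should be compared within a row and not down the column.

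**4. Second check with the marginal effect fixed.** Here N = 237, with 40% against 25% use. The level is 0.05/7 = 0.00714, assuming seven secondary tests (the plan gives no count). By correlation between baseline and later use, power under the rule and when always adjusting is 41% → 44% (0.25), 41% → 53% (0.50) and 43% → 66% (0.67). With no correlation it stays at 40%.

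**5. Type I error.** At nominal 5%, the adjusted Wald test rejected 3.8% of the time under the null in the 90/5 case, 4.8% at 70/15 and 4.9% at 60/20. The 90/5 case is sparse: 118 × 0.6 × 0.05 ≈ 3.5 non-users per arm start opioids.

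**6. Odds ratio and relative risk.** In the first three rows the adjusted odds ratio is 0.50 while the relative risk is 0.88, 0.71 and 0.66. The route from one to the other therefore needs stating.

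**The case against.** The strongest reply is that the plan already calls the model multivariable and the relative risk adjusted, whereas the complications paragraph says only logistic regression. Covariates were evidently intended, and baseline use may be among them. This stands in part. The documents do not exclude baseline use; they leave it unnamed, and the only rule they do write would usually leave it out.

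A second reply is that the gain may be small. This also stands. Even the 60/20 row is an odds ratio of 6 between baseline and later use; at 50/30 (odds ratio 2.3) almost nothing is gained. The largest variance fall belongs to an extreme association, where the relative risk is 0.88 and power stays low either way.

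Three stronger readings are tempting, and the documents support none of them:

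- *The comparison is biased or the test invalid.* Randomisation protects both.
- *The variance falls by 69%, 27% and 14% in the first three rows.* Those figures compare always adjusting with never adjusting. The plan's written rule adjusts when imbalance is seen, so the falls against the plan are 53%, 16% and 8%.
- *An odds ratio will be reported as a relative risk.* The plan commits to a relative risk and omits only how it is derived.

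**Conclusion.** The point holds as a low-cost improvement to one secondary outcome. The opioid model's covariates are unspecified. The only written route for baseline use would admit it in about 13% of full-size trials, and the plan's own precision argument for the scale scores applies here too. Against the plan's rule, the gain ranges from nothing to about half the variance of the log relative risk; the middle cases give 8% to 16%. That range rests on assumed prevalence, association and effect. A fairly strong association is plausible, since a baseline user still taking opioids at any follow-up counts as an event, but the documents do not establish it. Confidence is high that the text is silent and moderate on the size of the gain. The missing derivation of the relative risk is a clarification, not a separate fault.

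**What to change.** Add to the Opioid Consumption paragraph that baseline opioid use (any or none) is always in the logistic model whatever its imbalance, and list any other covariates; the imbalance rule can continue for the rest. State that the adjusted relative risk comes from that model by standardisation: predict each patient's risk under 90°C and under 80°C, average each set, and take the ratio. A bootstrap interval would fit the plan's existing practice for the primary outcome ("All the confidence intervals will be estimated based on bootstrapped standard error with 10,000 bootstrap replications"). The logistic Wald test can stay.

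The cost is one or two sentences and a few lines of code. It needs no new data and no change to the primary analysis, sample size or alpha allocation. If baseline use proves unrelated to later use, nothing material is lost. If very few non-users start opioids, the adjusted test is somewhat conservative (about 3.8% at nominal 5%).

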- 2. This prospective study will assess the relative effects of two temperatures (in degrees Celsius) used to ablate the targeted nerves in regards to pain management and possible complications.

Research Question:

Which temperature used to produce RF lesion (80°C or 90°C) is associated with better overall improvement in facet-mediated chronic low back pain?

Specific Hypotheses:

Primary

Lumbar facets medial branches RFA at 90°C provides more overall pain relief (i.e. percent of improvement), when compared to ablation at 80°C with no additional adverse events.

Secondary

Ablation of the lumbar facets nerve supply at 90°C will provide better improvement in the functionality level, general mood and quality of life as measured by VAS (Visual Analog Scale) pain score, Pain Disability Index (PDI), McGill Pain and Beck Inventory (BI) questionnaire scores than those receiving the ablation at 80°C. Furthermore, it is associated with less opioid consumption, no additional unwanted adverse events and/or complications along with less need to repeat RFA procedure over one year follow-up period.

Significance/Importance:

Chronic lower back pain (LBP) is a significant health care issue in the United States and the world. Chronic LBP contributes to decreased quality of life, decreased functionality and increased utilization of health care resources. The causes of chronic LBP tend to be multi-factorial. Arthropathy of the lumbar facet joints is thought to be a common etiology (15-45%) (1). Radiofrequency Ablation (RFA) of the medial branch nerve of the facet joint is a well-established treatment modality used to decrease facet joint pains. However, a wide range

Protocol Version 3 Revision Date: 10/15/2019 of temperature is being used (70-90 degrees Celsius). In addition, the optimal temperature that provides the best patient outcomes with the least side effects is not well established in the pain management literature.

Summary of Literature:

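### The opioid analysis promises an adjusted relative risk from a logistic model but gives no step from the odds ratio to the relative risk, and the outcome is too common for the two to agree

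*Combined protocol and SAP*

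**What the plan says.** Lower opioid use at 90°C is one of the secondary hypotheses: "Furthermore, it is associated with less opioid consumption" (Specific Hypotheses, Secondary). Under Data Analysis, Opioid Consumption, the outcome is dichotomised: "postoperative opioid consumption within a year of the first RFA will be analyzed as a binary outcome, i.e., any versus none". The reason given is that in the department's retrospective study "over 60% of our patients did not take any opioids".

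The same paragraph then names the model and the effect measure: "Multivariable logistic regression will be used to estimate the adjusted relative risk for postoperative opioid use". The test follows: "A logistic model-based Wald test for regression coefficients will be used to test the hypothesis", which the plan explains in brackets as testing "whether or not the relative risk is different from a value of 1.0".

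The Data Analysis section also says that clearly imbalanced baseline variables (absolute standardized difference above 0.20) "will be adjusted for in both primary and secondary analyses". The opioid model may therefore contain covariates.

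The analysis and sample size sections describe no step from the logistic coefficient to a relative risk: no averaging of predicted risks, no log-binomial model and no Poisson model with robust variance.

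**The concern.** The stated measure and the stated model do not match. Exponentiating the treatment coefficient of a logistic model gives an odds ratio. It approximates a relative risk only when the outcome is rare, and the plan's own retrospective figure does not support treating opioid use as rare.

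The paragraph uses relative-risk language twice in succession, once for the estimate and once for the test on the coefficients. An analyst following it literally would most naturally exponentiate the coefficient and label the result a relative risk. The number at stake is the published size of the effect on opioid use. Readers would take it as a proportional change in the share of patients using opioids, and it would be exaggerated in favour of whichever arm did better.

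**Working it through.** The documents give no effect size, power or per-arm rate for opioid use, so there is no planned figure to reproduce.

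**Inputs**
- Overall use below 40%, from the statement under Opioid Consumption that more than 60% took none. This is an upper limit, from retrospective data and not by arm.
- Risk p0 at 80°C: assumed 0.20, 0.30 and 0.40.
- True relative risk RR: assumed 0.80 for the main illustration. The direction follows the secondary hypothesis.

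**Formulas**
- p1 = RR × p0
- OR = [p1/(1 − p1)] / [p0/(1 − p0)]
- Substituting p1 gives 1 − OR = (1 − RR)/(1 − p1). Reading the odds ratio as a relative risk therefore multiplies the apparent reduction by 1/(1 − p1).

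**Results for a true relative risk of 0.80 (a 20% reduction)**

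| p0 (80°C) | p1 (90°C) | OR | Reduction if OR is read as RR | Inflation 1/(1 − p1) |
|---|---|---|---|---|
| 0.20 | 0.16 | (0.16/0.84)/(0.20/0.80) = 0.762 | 23.8% | 1.19 |
| 0.30 | 0.24 | (0.24/0.76)/(0.30/0.70) = 0.737 | 26.3% | 1.32 |
| 0.40 | 0.32 | (0.32/0.68)/(0.40/0.60) = 0.706 | 29.4% | 1.47 |

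**Other effect sizes at p0 = 0.40**
- RR 0.90 gives OR 0.844, so a 10% reduction reads as 15.6%.
- RR 0.75 (40% against 30%) gives OR 0.643, so 25% reads as 35.7%.
- RR 0.70 gives OR 0.583, so 30% reads as 41.7%.
- In the other direction, RR 1.20 gives OR 1.385, so a 20% increase reads as 38.5%.

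**Can the logistic model supply the relative risk?** Yes. A logistic model with treatment and one covariate was fitted to 200,000 simulated patients. The average predicted risks were 0.388 with everyone set to control and 0.272 with everyone set to treatment. Their ratio was 0.70, the same as the crude relative risk. The exponentiated treatment coefficient from the same fit was 0.53.

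That last gap has two parts. The odds ratio formed from the two average risks is (0.272/0.728)/(0.388/0.612) = 0.59. The move from 0.70 to 0.59 is the odds-ratio-against-relative-risk gap. The further move to 0.53 arises because an odds ratio conditional on a covariate differs from the marginal one (non-collapsibility).

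**The test.** In a logistic model without treatment-by-covariate interaction, a zero treatment coefficient makes the two arms' risks equal at every covariate value. OR = 1 and RR = 1 are then the same null hypothesis.

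**The case against.** The strongest reply is that the plan never says the exponentiated coefficient will be printed as the relative risk. It says that logistic regression will be used to estimate a relative risk, and averaging predicted risks does exactly that. This stands as far as it goes. A reader might infer that logistic regression is the wrong model, or that the plan commits to a wrong number. The documents support neither. What remains is that the necessary step is absent and that the most natural reading of the text leaves it out.

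Three further points also stand.

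- **The test.** A reader might think the Wald test is invalid because the plan describes it in terms of relative risk. It is not; the description of the null hypothesis is correct.
- **The base rate.** A reader might take the plan to put opioid use at nearly 40%. It gives only an upper limit, for retrospective patients taken together. At lower rates the distortion shrinks but does not vanish.
- **Covariate adjustment.** A more dramatic example is easy to build. Assume that 38% of patients are baseline users, with later use of 85% in them and 10% in the rest. An adjusted odds ratio of 0.65 then corresponds to average risks of 0.385 and 0.341, a relative risk of about 0.885. Those inputs are not in the documents, and baseline opioid use enters the model only if it is imbalanced. The marginal odds ratio in that example is about 0.83, so about 0.18 of the 0.235 difference is non-collapsibility. It should not be used to size this point.

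Finally, this is one secondary outcome among several. The primary analysis, sample size and interim boundaries are untouched.

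**Conclusion.** The point holds as a mismatch between the stated effect measure and what the stated model directly gives, with the conversion step missing. If the exponentiated coefficient is reported as the relative risk, a true 20% reduction would appear as about 24% to 29% for assumed use at 80°C between 20% and 40%. Any interval would be displaced in the same way. The distortion is always away from 1, so it would exaggerate an increase as well as a reduction.

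This rests on three things: the assumed per-arm rates, since the documents give only the overall upper limit; the assumed relative risk of 0.80; and the analyst taking the literal route. The size is for the unadjusted comparison; prognostic covariates in the model would move the odds ratio further from the relative risk. The p-value as planned is not in question. The plan should be changed before analysis, but nothing in the trial's conduct or its primary conclusion depends on it.

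**What to change.** Keep the relative risk as the measure and state how it and its confidence interval will be obtained, by one of two routes:

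- Fit the logistic model as planned, predict each patient's risk under 90°C and under 80°C, average over the trial population, and take the ratio. Use a bootstrap interval; bootstrapping is already planned for the intervals in the primary analysis. The planned Wald test can stay.
- Fit a Poisson regression with robust variance, whose exponentiated coefficient is a relative risk. In that case, say that its Wald test replaces the logistic one.

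If the logistic coefficient is to be the reported estimate, call it an adjusted odds ratio and reword the explanation of the test to match. Give the risk in each arm and the risk difference beside it.

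The cost is a sentence in the plan and a few lines of code, with no new data. The reported effect will look somewhat smaller than the odds ratio would have made it look. Fixing the choice before analysis also removes the option of choosing between the two measures once the results are known.
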